## 2.5 Correlative Studies Background (Treatment Group 1)

The proposed trial provides a rich context for the investigation of biomarkers for anti-PD1 therapy. Treatment of cutaneous T cell lymphomas with MK-3475 (pembrolizumab) monotherapy produced a response rate of ~33%, and we expect that the addition of interferon gamma will result in an even higher rate of clinical response. This high rate of response will improve our statistical power in discovering novel biomarkers. Additionally, as a cutaneous malignancy with frequent leukemia, CTCL affords the opportunity for serial collection of high quality biopsies of skin and blood. Thus, from an exploratory biomarker perspective, this disease offers an opportunity to investigate the determinants of response and resistance to anti-PD-1 and immune therapies, as well as to discover additional molecular targets governing immune dysregulation in cancer.

Correlates will focus on potential predictive biomarkers for PD-1 therapy (e.g., as expression of PD-L1 and mutational/neoantigen burden) and assessment of the effects of IFN-gamma (e.g., Th1 vs Th2 skewing). The addition of interferon gamma is hypothesized to affect the tumor microenvironment in two ways: 1) IFN-gamma will upregulate PD-L1 expression on suppressive cell populations. 2) IFN-gamma will skew CD4 T cells towards a Th1 phenotype. Sampling time points have been selected to explore these effects.

The majority of proposed biomarkers are designed to be hypothesis-generating by applying novel technologies such as multiple ion beam imaging and CyTOF to provide means to analyze the effects of checkpoint blockade both systemically and in the tumor microenvironment in an unprecedented manner. We anticipate that these studies will yield candidate biomarkers that correlate with prognosis, have predictive value in the selection of which subjects benefit from anti-PD1/IFN-gamma immunotherapy, and will investigate the hypothesis that Th1 skewing of the T cell repertoire can potentiate immune checkpoint blockade therapy.

Assays may include but are not be limited to:

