**Table 9.1 Tumor Tissue and Blood Collection**

		Response (PR/CR)/PD	EOT and Skin Flare Rxn
5 mm punch biopsies*	Required at baseline — (Sent to CITN Central Lab in formalin) and at C1D1 and C2D1	Required at progression or appearance of a new lesion — (Sent to CITN Central Lab in formalin)  Optional at response (PR/CR)	Required – (Sent to CITN Central Lab in formalin)
Image guided Core Biopsy (subjects with known LN disease only)	Optional – (Core biopsy to CITN Central Laboratory in Formalin)	Optional – (Core biopsy to CITN Central Laboratory in Formalin)	Optional – (Core biopsy to CITN Central Laboratory in Formalin)
Biomarkers (blood)	Required (Sent to CITN Central Lab) timing of specific biomarkers are variable, see study calendar	Required for both response and PD (Sent to CITN Central Lab)	Required (Sent to CITN Central Lab)
Biorepository: 30 mL total volume. (20 mL for PBMCs and 10 mL for Serum)	Optional (Sent to CITN Central Lab) at screening, then every 3rd cycle	Optional (Sent to CITN Central Lab)	Optional (Sent to CITN Central Lab)

\*Any tissue remaining after testing has been completed will be stored in the CITN Central Laboratory Biorepository for storage and future testing if the patient has given permission in the consent form.

\*\*All blood that is drawn for storage in the Biorepository will be shipped to the CITN Central Laboratory Biorepository for storage and future testing.

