#### 13.1.1.3 *Exploratory Objectives*

To investigate the relationship between the following putative biomarkers for combination immunotherapy of MK-3475 (pembrolizumab) and IFN-gamma (Actimmune®) and clinical outcomes (as measured by safety/tolerability and ORR, DOR, PFS, EFS) in subjects with previously treated Mycosis Fungoides/Sézary Syndrome, including tumor/microenvironment (PD-1/PD-L1/PD-L2 expression, CTLs, Tregs, macrophages, DCs; nanostring gene expression profile), systemic immune response (flow cytometry, CyTOF, Luminex multiplexed cytokine profile), and molecular/genomic immune correlates (exome sequencing, high throughput sequencing (HTS) for TCR).

**Hypothesis:** The putative biomarkers and immune regulators tested will be related to clinical response induced by combination immunotherapy of MK-3475 (pembrolizumab) and IFN-gamma (Actimmune®) and will help define actionable causes of not achieving CR.

The primary and key secondary endpoints, primary analysis population, and statistical methods that will be employed for the efficacy analyses are presented in the Table below.

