#### 13.1.2 Exploratory Correlative Analyses

Clinical response (as measured by the primary and secondary endpoints) to combination immunotherapy regimen as a function of biomarkers will be evaluated. All biomarker assays will be run on the clinical trial samples in a blinded manner.

Time to event endpoints (DOR, PFS, EFS) will be evaluated using Kaplan-Meier curves generated by biomarker scoring group using the log-rank test.

Exploratory outcomes will be summarized with descriptive statistics (primarily proportions and medians) for all biomarkers described above, and additionally, serum IL-10, regulatory T-cells, and activated CD8 T cells. Scatterplots and Kendall's tau estimates will be produced for estimating correlation of PD-1, PDL1, or PD-L2 expression measures and clinical outcome across compartments (skin, lymph node, blood). Comparison of tissue IHC markers between pre-treatment and with clinical response or disease progression will be assessed using Wilcoxon signed-rank test. A full panel of approximately ~600 mRNA transcripts will be measured using the Nanostring platform and will be evaluated using descriptive statistics.

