## APPENDIX C BIOASSAY TEMPLATES

### Mycosis Fungoides/Sézary Syndrome (Treatment Group 1)

Biomarker Name a AND Lead PI and Site	Assay (CLIA: Y/N)	Use (Integral, Integrated, or Exploratory) AND Purpose b	Tissue/Body Fluid Tested and Timing of Assay	M/O	Funding Source(s) c
Tissue PDL1 Expression  PI: [name]  Site: Fred Hutchinson Cancer Research Center	Chromagenic (Single-Color) IHC for PD-L1  CLIA: N	Exploratory  Purpose: We will explore correlation of PDL1 expression with response. Two hypotheses will be explored:  1) Pre-treatment PDL1 expression correlates with response  2) Interferon-gamma mediated upregulation of PDL1 correlates with response	Tissue: Skin biopsy  Timing:  (M) Prior to IFN-gamma lead-in, Prior to Cycle 1, Prior to Cycle 2, w at progression or appearance of a new lesion, at end of treatment, and in the event of a Skin Flare Reaction  (O) At response (PR/CR),	M	Funding for biomarkers will be from CITN with co-funding from Merck and Horizon. Additional funds will be sought from foundations and CTEP's CRADA with Merck
Spatial association of tumor cells and components of the tumor microenvironment  PI: [name]  Site: Fred Hutchinson Cancer Research Center	Multispectral immunohistochemistry  CLIA: N	Exploratory  Purpose: Hypothesis generating  Multispectral immunohistochemistry IHC for PD1, PDL1, PDL2, CD3, CD4, CD8, Foxp3, CD163 will define the spatial relationship of the tumor infiltrate	Tissue: Skin biopsy  Timing:  (M) Prior to IFN-gamma lead-in, Prior to Cycle 1, Prior to Cycle 2, at progression or appearance of a new lesion, r, at end of treatment, and in the event of a Skin Flare Reaction  (O) At response (PR/CR),	M	(see above)
High dimensional imaging of tumor microenvironment  PI: [name]  Site: Stanford University	Multiplexed Ion Beam Imaging  CLIA: N	Exploratory  Purpose: Hypothesis generating  Mass spectroscopy based imaging of ~30 parameters simultaneously to delineate expression of immune checkpoint molecules and activation markers on components of the tumor microenvironment	Tissue: Skin biopsy  Timing:  (M) Prior to IFN-gamma lead-in, Prior to Cycle 1, Prior to Cycle 2, , at progression or appearance of a new lesion, at end of treatment and in the event of a Skin Flare Reaction  (O) At response (PR/CR).	M	(see above)

NCI Protocol #: CITN-13  
 Version Date: March 03, 2020

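### Section 13.1.2 names no test of any Group 1 tissue IHC marker against response versus non-response; the one test assigned specifically to these markers measures change within patients

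*Combined protocol and SAP*

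**What the plan says.** Section 13.1.1.3 states the Group 1 hypothesis: "The putative biomarkers and immune regulators tested will be related to clinical response induced by combination immunotherapy". Section 13.1.2 opens in the same spirit: "Clinical response (as measured by the primary and secondary endpoints) to combination immunotherapy regimen as a function of biomarkers will be evaluated". Appendix C gives two hypotheses for PD-L1: that its pre-treatment level correlates with response, and that "Interferon-gamma mediated upregulation of PDL1 correlates with response".

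Section 13.1.2 then names these tools:

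- Log-rank: "Time to event endpoints (DOR, PFS, EFS) will be evaluated using Kaplan-Meier curves generated by biomarker scoring group using the log-rank test". This is not tied to any assay.
- Scatterplots and Kendall's tau estimates of PD-1, PD-L1 and PD-L2 against clinical outcome. No test or interval is stated.
- For tissue IHC: "Comparison of tissue IHC markers between pre-treatment and with clinical response or disease progression will be assessed using Wilcoxon signed-rank test".
- Descriptive statistics for all biomarkers.

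Sections 2.5.2 and 9.1.2.2 list CD3, CD4, CD8, Foxp3 and CD163 as IHC markers in addition to the three checkpoint markers. Table 9.1 requires skin biopsies at baseline, C1D1, C2D1 and progression. At response the biopsy is optional.

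**The concern.** The hypothesis concerns differences between patients: do those who respond have a different marker level, or a different change in it, from those who do not? The signed-rank test on pre-treatment and later samples has another null, that within-patient changes are symmetric about zero. The protocol expects a treatment effect on at least one marker whatever the outcome: Section 2.5 says that "IFN-gamma will upregulate PD-L1 expression on suppressive cell populations". A significant signed-rank result can therefore be purely pharmacodynamic.

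The timing adds difficulty. Because the response biopsy is optional, the response pairs are self-selected and may be few. Complete response in skin means full clearance of lesions (Section 11.1.1.6), and the malignant cells are typically CD4+ (Section 9.1.1.4). A fall in CD3 or CD4 staining at that visit may simply be the response itself.

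At stake is how the results are read. Section 2.5 hopes these data will yield candidate predictive markers. A shift common to all patients, reported as related to response, would misdirect later work. A marker that moves in opposite directions in responders and non-responders could be missed if the pairs are pooled.

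**Working it through.** **Inputs.** Section 13.1.2 gives no alpha, power or number of pairs, so there is no planned figure to reproduce. From Section 13.1.1.4: at most 30 patients, and 17 responders at the success boundary, giving a 17/13 split. The design rates give the range: 0.37 × 30 = 11.1 (11/19) and 0.65 × 30 = 19.5 (20/10). Assumptions not in the documents: two-sided 5%, normal within-patient changes with SD 1, one usable pair per patient, and the shift sizes. Simulations used 4,000 replicates per setting.

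**Why a common shift triggers the signed-rank test.** With n changes, the null mean of W+ is n(n+1)/4 and its variance is n(n+1)(2n+1)/24. For n = 30 these are 232.5 and 2363.75 (SD 48.6). Under a common shift δ, E(W+) = [n(n−1)/2]·Φ(√2·δ) + n·Φ(δ).

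- δ = 0.5: 435 × 0.760 + 30 × 0.691 = 351.4, which is (351.4 − 232.5)/48.6 = 2.4 null SDs above the null mean.
- δ = 0.25: 435 × 0.638 + 30 × 0.599 = 295.6, which is 1.3 null SDs above.

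Response status appears nowhere in these formulas. The rank-sum test uses differences between a responder's change and a non-responder's change, so a common δ cancels.

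**Rejection under a common shift with no relation to response (simulated).**

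| Pairs in the signed-rank test | 0.25 SD | 0.5 SD | 0.75 SD | 1 SD |
|---|---|---|---|---|
| 11 | 10% | 30% | 58% | 81% |
| 17 | 14% | 46% | 80% | 96% |
| 20 | 17% | 54% | 87% | 98% |
| 30 | 24-25% | 73-74% | 97% | 99.8-100% |

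The rank-sum test of change, responders against non-responders, rejects in 4-5% at every shift and in all three splits.

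**Separate tests by group.** At a common 0.5-SD shift and a 17/13 split, the signed-rank test rejects in 46% of trials among responders and 36% among non-responders. The two results disagree in 49% of trials although the groups do not differ. Significance in one group and not in the other is not evidence of association.

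**Real associations, 17/13 split.**

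- 1-SD shift in responders only: pooled signed-rank 77%, rank-sum 73%. The 77% is close to the 73% seen for a 0.5-SD shift common to everyone, so a significant pooled result hardly separates the two situations.
- Opposite shifts averaging zero, +0.5 SD in responders and −0.5 × 17/13 = −0.65 SD in non-responders: pooled signed-rank 2%, rank-sum 83%.
- Opposite shifts of +1 and −1.31 SD: pooled signed-rank 0.2%, rank-sum about 100%.

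**Coverage of the other tools.** The log-rank test relates marker groups to DOR, PFS and EFS. DOR is analysed in responders only (efficacy table in Section 13.1.1.3), so it cannot address response against non-response. PFS and EFS use all evaluable patients but are different outcomes from ORR, and no cut-points for the groups are given. Kendall's tau addresses response for three markers, as an estimate. For the other five IHC markers, what remains is this generic log-rank test and descriptive statistics.

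**The case against.** The strongest reply is that Section 13.1.2 contains more than the signed-rank test. The log-rank sentence is not limited to any assay, Section 13.1.1.3 lists tissue markers among the biomarkers and PFS and EFS among the outcomes, so a between-patient test that can include CD8, Foxp3 and CD163 is planned. PD-L1, the marker with the clearest expected shift, has Kendall's tau against outcome. A reader might infer that the signed-rank test is the only analysis linking IHC markers to outcome; the documents do not support that.

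Nor does the plan say that the signed-rank test is meant to test the hypothesis in Section 13.1.1.3. The sentence describes a paired comparison over time, for which the test is standard. Appendix C describes the multispectral IHC panel as hypothesis-generating and gives it no response hypothesis of its own. The plan also does not say that response and progression pairs will be pooled, so the low pooled power against opposite shifts depends on that assumption.

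A reader might also infer that the test rejects whenever treatment moves a marker. It does not: at 0.25 SD it rejects in about a quarter of trials with 30 pairs, and less often with fewer.

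All of this stands, and it narrows the point. It does not supply a comparison of responders with non-responders, which is the most direct form of the stated hypothesis.

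**Conclusion.** The point holds in limited form. No test of any tissue IHC marker against response versus non-response is named, and CD3, CD4, CD8, Foxp3 and CD163 have no response-specific association measure. The one test assigned specifically to tissue IHC markers cannot establish that a marker is related to response. Under a common 0.5-SD shift with no association it rejects in about 30% of trials with 11 pairs and 73% with 30. These sizes rest on the assumed shifts, normal changes, 5% level and number of pairs. The logical mismatch does not.

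Severity is minor. Section 2.4.5 states that the correlative studies are exploratory and are not endpoints, and no stopping rule, success criterion or patient-level decision uses them.

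**What to change.** In Section 13.1.2, state that each tissue IHC marker's baseline level, and its change from pre-lead-in to C1D1 and to C2D1, will be compared between confirmed responders and non-responders with a Wilcoxon rank-sum test. Report the difference with a 95% CI and label it exploratory and unadjusted for multiplicity. Baseline level is needed because Appendix C hypothesises it for PD-L1. Keep the signed-rank test as a description of pharmacodynamic change, and say that it does not test association with response.

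The cost is a few sentences. The baseline, C1D1 and C2D1 skin biopsies are already required and precede the first global assessment at cycle 6, so no samples or visits are added.

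There are two drawbacks. With at most 30 patients only large differences are detectable: for a 1-SD shift in responders only, simulated power is 73% (17/13), 66% (20/10) and 68% (11/19). Several tests are also added: eight markers by three comparisons is 24 per compartment, or 24 × 0.05 = 1.2 expected false positives at 5% if no marker is related to response. Hence the emphasis on intervals and the exploratory label.

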#### 13.1.3 Sample Size/Accrual Rate

##### 13.1.3.1 *Power and Sample Size*

The statistical criterion for success requires ORR that is greater than 37% (null) and at least 65% (alternative). By adding an interim futility analysis, the sample size is 30

patients. The probability of stopping at interim futility analysis under the null and alternative are 52% and 2%, respectively. The type I error rate is 2%. The power is 87%. The expected sample sizes under the null and alternative are 21 and 30, respectively.

This is a single stage trial. Patients will be recruited continuously. We will perform the interim futility analysis when 12 patients have been followed for 6 months. If ORR is less than 33% (4 or less CR+PR), the trial will stop and we will accept the null that combination therapy is no better than monotherapy. Otherwise, the trial will continue until we reach 30 patients. If ORR is at least 57% (17 or more CR+PR) at the final analysis, we will accept the alternative that combination therapy is significantly better than monotherapy.

#### PLANNED ENROLLMENT REPORT

Racial Categories	Ethnic Categories				Total
	Not Hispanic or Latino		Hispanic or Latino		
	Female	Male	Female	Male	
American Indian/Alaska Native					
Asian	1	1			2
Native Hawaiian or Other Pacific Islander					
Black or African American	1	1			2
White	7	17	1	1	26
More Than One Race					
Total	9	19	1	1	30

PHS 398 / PHS 2590 (Rev. 08/12 Approved Through 8/31/2015) OMB No. 0925-0001/0002

#### 13.1.4 Stratification Factors

There is no planned stratification.

#### 13.1.5 Reporting and Exclusions

##### 13.1.5.1 *Evaluation of Toxicity*

All patients will be evaluable for toxicity from the time of their first treatment with Interferon-gamma or MK-3475 (pembrolizumab).

##### 13.1.5.2 *Evaluation of Response*

All patients included in the study must be assessed for response to treatment, even if there are major protocol treatment deviations or if they are ineligible. Each patient will be assigned one of the following categories: (1) complete response, (2) partial response, (3) stable disease, (4) progressive disease, (5) early death from malignant

disease, (6) early death from toxicity, (7) early death because of other cause, or (9) unknown (not assessable, insufficient data). [Note: By arbitrary convention, category 9 usually designates the “unknown” status of any type of data in a clinical database.]

All of the patients who met the eligibility criteria (with the possible exception of those who received no study medication) should be included in the main analysis of the response rate. Patients in response categories 4-9 should be considered to have a treatment failure (disease progression). Thus, an incorrect treatment schedule or drug administration does not result in exclusion from the analysis of the response rate. Precise definitions for categories 4-9 will be protocol specific.

All conclusions should be based on all eligible patients. Subanalyses may then be performed on the basis of a subset of patients, excluding those for whom major protocol deviations have been identified (e.g., early death due to other reasons, early discontinuation of treatment, major protocol violations, etc.). However, these subanalyses may not serve as the basis for drawing conclusions concerning treatment efficacy, and the reasons for excluding patients from the analysis should be clearly reported. The 95% confidence intervals should also be provided.

## 13.2 Synovial Sarcoma (Treatment Group 2)

### 13.2.1 Study Endpoints

The primary objective is to determine whether the combination of interferon gamma-1b (ACTIMMUNE®) and MK-3475 (pembrolizumab) improves the overall response rate (ORR) of pembrolizumab in patients with unresectable or metastatic synovial sarcoma.

The ORR of single agent pembrolizumab is  $\leq 5\%$ . Accordingly, a Simon 2-stage design will be used: Twelve patients will be enrolled initially. If 0 respond the study will be stopped for futility. Otherwise, an additional four patients will be enrolled. If three or more out of 16 patients respond, the treatment will be considered promising and would likely lead to widespread use of this regimen in the clinic.

The secondary objectives for the study are:

- To determine the progression-free survival (PFS) and overall survival (OS) for patients with advanced synovial sarcoma receiving interferon gamma-1b and MK-3475 (pembrolizumab).
- To determine the tolerability of the combination of interferon gamma-1b and MK-3475 (pembrolizumab) based on CTCAE version 5.0

The exploratory objectives are to investigate paired, serial biopsy specimens from pre-treatment and 8-12 weeks after starting treatment for the following:

- MHC class I expression (scored by pathologist)
- Number of infiltrating T cells per mm^2
- Tumor associated macrophage number and phenotype using multiplex immunohistochemistry
- T cell clonality
- Gene expression profiling

Additionally, the exploratory objectives include investigating peripheral blood samples from patients to determine:

- The number and phenotype of T cells specific for CT antigens and potential neo-antigens
- The phenotype of circulating monocytes
- Cytokines associated with response

The primary and key secondary endpoints, primary analysis population, and statistical methods that will be employed for the efficacy analyses are presented in the table below.

### Summary Analysis Strategy for Efficacy Endpoints

Endpoint/Variable	Statistical Method	Analysis Population	Missing Data Approach
Primary:			
Overall Response Rate (ORR)	Binomial proportion	Evaluable population as defined	Subjects without any efficacy evaluation will be excluded; if one compartment is missing data, that compartment will be considered non-response.
Secondary:			
Progression-free survival (PFS)	Kaplan-Meier method	All efficacy or safety evaluable patients	Censored at last follow-up or start of new significant therapy
Overall survival (OS)	Kaplan-Meier method	All efficacy or safety evaluable patients	Event is death due to any cause, otherwise it is considered censored at last follow-up
Tolerability	Binomial proportion	All enrolled patients	All AEs and SAEs will be summarized

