Toxicity will be assessed by CTCAE v. 5.0. Although interferon gamma-1b in combination with MK-3475 (pembrolizumab) has previously been seen to be safe, its side effect profile has not been confirmed in a synovial sarcoma patient population or in a population of patients with cold tumors. There is no reason to suspect there would be additional toxicity in these patients however, we will adopt CTEP's data safety monitoring plan of every two week teleconferences attended by all participating site principal investigators, CTEP staff and CITN Coordinating Center staff to oversee the safety of the trial. During each activated protocol teleconference all patient toxicities, including all serious adverse events (SAE) and all other clinical data will be reviewed. Any SAE suspected to be attributed to the study regimen will be distributed to all participating site principal investigators and their staff on an urgent basis. If necessary, an ad hoc teleconference may be convened to discuss any adverse event determined to be a patient safety issue or if the adverse event is suspected of being related to study treatment.

Radiographic assessment by CT scan will occur every 12 weeks. Response and progression will be determined using RECIST v1.1. All patients with either a CR, PR or stable disease (SD) will continue therapy for up to two years. Patients will be followed for up to two years after study discontinuation for disease status and survival. Patients with radiographic progression but who are otherwise stable without symptomatic progression may continue treatment up until confirmation at the next radiographic imaging time point in order to assess for possible pseudo progression. ORR based on immune related response criteria (IRRC) will also be noted as an exploratory endpoint.

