#### 9.2.2 Research Biopsies for Correlative Studies

A mandatory research biopsy will occur prior to the initiation of study therapy. There is no time limit on the pretreatment biopsy. However, the patient cannot have undergone a different therapy since its collection. Archival tissue can be used in lieu of a pretreatment biopsy if the patient has not undergone any treatment since that tissue was collected. Archival tissue may also be used in lieu of a fresh biopsy for patients <18. The second biopsy is mandatory for participant  $\geq 18$  years of age, but will be performed only if deemed safe by the principal investigator. For participants <18 years of age a second biopsy is optional and will only be performed if deemed safe by the principal investigator. The second biopsy will be performed after Week 8 but before the patient's first scan which will occur 12 weeks after starting treatment. Multiplex immunohistochemistry of tumor biopsy samples will test whether clinical outcomes correlate with the level of increased MHC expression, T cell infiltration and the presence of other immune infiltrates on paired biopsy specimens. Gene expression using the NanoString platform will be used to determine whether increased expression of inflammatory markers at 8-12 weeks correlates with clinical outcomes.

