### 13.2.2 Interim Safety and Futility Analyses

One interim safety analysis will be performed in this study when 12 patients are evaluable for toxicity at pre-C4 (week 10) of the study. If at that time, 4 or more patients have experienced unexpected study drug related serious adverse events (SAEs), we will conclude that the combination immunotherapy regimen is too toxic and accrual will stop.

The properties of interim safety stopping rules are given in the table below.

True Probability of Study Drug-Related SAEs (ptox)	Probability of Stopping Early
0.10	0.026
0.14	0.075
0.18	0.155
0.22	0.261
0.26	0.382
0.30	0.507

One interim futility analysis will be performed in this study. A Simon 2-stage design will be used: Twelve patients will be enrolled initially. If 0 respond the study will be stopped for futility. The probabilities of stopping the trial for futility at this interim analysis are 54% and 3% under the null hypothesis (ORR=5%) and alternative hypothesis (ORR=25%) respectively.

Otherwise an additional four patients will be enrolled. If three or more out of 16 patients respond, the treatment will be considered promising and would likely lead to widespread use of this regimen in the clinic.

The overall type I error for the study is 4.3%, and the overall power of the study at the alternative hypothesis (ORR=25%) is 80.1%.

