#### 13.2.4 Sample Size and Power

A Simon 2-stage design will be used: Twelve patients will be enrolled initially. If 0 respond the study will be stopped for futility. The probabilities of stopping the trial for futility at this interim analysis are 54% and 3% under the null hypothesis (ORR=5%) and alternative hypothesis (ORR=25%) respectively.

Otherwise, an additional four patients will be enrolled. If three or more out of 16 patients respond, the treatment will be considered promising and would likely lead to widespread use of this regimen in the clinic. The overall type I error for the study is 4.3%, and the overall power of the study at the alternative hypothesis (ORR=25%) is 80.1%.

The patient demographics for the addendum is expected to be similar to the patient demographics of the original protocol. The planned enrollment report is given below.

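### Group 2's primary ORR excludes treated patients with no efficacy evaluation, so deaths before the first scan leave the denominator and the reported rate can only be pushed upward

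*Combined protocol and SAP*

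**What the plan says.** Section 13.2.1 introduces a table of populations and methods for the Group 2 efficacy endpoints. Its ORR row specifies a binomial proportion in an evaluable population that is referred to as already defined. The missing-data entry is: "Subjects without any efficacy evaluation will be excluded". It then adds that a compartment with missing data is taken as non-response.

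Neither section 11.2 nor section 13.2 defines that population. The response table in 11.2.2 covers complete and partial response, stable disease, progression and relapse. It has no category for early death or for a patient who cannot be assessed.

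On timing, section 9.2.2 refers to the "first scan which will occur 12 weeks after starting treatment", and section 5.2.2 says "Radiographic assessment by CT scan will occur every 12 weeks".

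The Simon design is written on enrolled patients. Section 13.2.2 says: "Twelve patients will be enrolled initially. If 0 respond the study will be stopped for futility". Four more are then enrolled, and section 13.2.4 gives the success rule: "If three or more out of 16 patients respond, the treatment will be considered promising".

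**The concern.** A patient without an efficacy evaluation cannot be a documented responder. Among treated patients, the exclusion therefore removes only non-responders, and the error has one direction.

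The rule is likely to be used. Section 3.1.2 admits patients with metastatic or unresectable disease after at least one line of chemotherapy, with ECOG status up to 2 and a required life expectancy of 12 weeks or more. The first scheduled scan comes at that same 12-week mark. A patient who dies earlier counts as an event for PFS and OS, whose rows in the same table use all patients evaluable for efficacy or safety, yet disappears from the primary endpoint.

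No other text repairs this for Group 2. The instruction to treat progression, early death and unknown status as failure is in 13.1.5.2, under the Group 1 heading, and section 13.2 does not refer to it. The compartment clause matches the Group 1 table and has no meaning under RECIST, which suggests that the row was carried over without adaptation.

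At stake is the ORR estimate that will be set against the 5% null and the 25% target in a cohort of 16. Its denominator would differ from the 12 and 16 on which the design is built.

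**Working it through.** **1. The plan's own figures.** Inputs from 13.2.2: n1 = 12, stop at 0 responses, n = 16, success at 3 or more, null 5%, alternative 25%.

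- Early stopping is (1 − p)^12: 0.95^12 = 0.540 and 0.75^12 = 0.032. The plan states that these "are 54% and 3% under the null hypothesis (ORR=5%) and alternative hypothesis (ORR=25%) respectively".
- Success is P(X1 ≥ 3) + P(X1 = 2)·P(X2 ≥ 1) + P(X1 = 1)·P(X2 ≥ 2), with X1 from 12 patients and X2 from 4.
- At p = 0.05: 0.0196 + 0.0988 × 0.1855 + 0.3413 × 0.0140 = 0.0427.
- At p = 0.25: 0.6093 + 0.2323 × 0.6836 + 0.1267 × 0.2617 = 0.8013.

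Both agree with the stated 4.3% and 80.1%. These figures hold when all 12 and all 16 patients are counted.

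**2. Effect on the estimate, 16 treated and no replacement.** With x responders and m exclusions, the reported ORR is x/(16 − m). The documents do not give m, so it is assumed. For x = 3, with exact 95% intervals:

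| Excluded (m) | Reported ORR | Exact 95% CI |
|---|---|---|
| 0 | 3/16 = 18.8% | 4.0% to 45.6% |
| 1 | 3/15 = 20.0% | 4.3% to 48.1% |
| 2 | 3/14 = 21.4% | 4.7% to 50.8% |
| 3 | 3/13 = 23.1% | 5.0% to 53.8% |
| 4 | 3/12 = 25.0% | 5.5% to 57.2% |

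**3. A rough scale for m.** Section 2.2 quotes a median survival of about 16 months. Assuming exponential survival, the share dead by week 12 (2.76 months) is 1 − 0.5^(2.76/16) = 11.3%, or 1.8 of 16. This is only an illustration. The life-expectancy criterion should lower it, and missed off-treatment scans would add to it.

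**4. Effect on the decision.** Success is a count of responders. Removing non-responders from a fixed set of 16 leaves that count unchanged, so 4.27% and 80.1% also stay unchanged.

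**5. Conditional case: excluded patients replaced until 12 and 16 are evaluable.** If a share d is unevaluable and all of them are non-responders, the response rate among evaluable patients is p/(1 − d). Putting 0.05/(1 − d) through the formula in step 1:

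| Assumed d | Rate among evaluable | Type I error |
|---|---|---|
| 10% | 5.6% | 5.5% |
| 20% | 6.3% | 7.4% |
| 30% | 7.1% | 10.1% |

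**The case against.** The strongest reply is that the decision is untouched. Each statement of the stopping and success rules counts enrolled patients, the cohort size is fixed at 16, and no Group 2 replacement rule exists. A reader might infer from the exclusion rule that type I error is inflated. The documents do not support that. The figures in step 5 need a replacement procedure, or a reading of 12 and 16 as evaluable patients, that the plan does not contain. This part of the objection stands.

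A reader might also infer that every patient with clinical progression before week 12 is lost. That is too strong. The Group 2 calendar (10.2) appears to schedule imaging at end of treatment or documented progression, although its columns are broken in the text available. Section 5.5 waives an assessment at discontinuation only when one was done in the preceding 4 weeks, which implies that one is otherwise expected. A progressing patient who is scanned on stopping stays in as progressive disease. The sure loss is deaths before any scan. Missed off-treatment scans add to it, and 11.2.1 leaves the scans partly to the site investigator's discretion. This part stands too.

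The size is also uncertain. Four exclusions of 16 is more than twice the 1.8 from the survival illustration, and with two exclusions the shift from 18.8% to 21.4% is small beside an interval of 4.0% to 45.6%. That limits the weight of the point. It does not justify the rule, because the bias is one-sided and avoidable.

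**Conclusion.** The concern holds for the estimate, not for the decision rule. Followed as written, the Group 2 ORR row removes treated failures who have no scan. It uses an undefined population and a denominator that can differ from the enrolled 12 and 16. With three responders, the reported ORR would rise from 18.8% to between 20.0% and 25.0% for one to four exclusions, and both confidence limits would rise with it. The number excluded is an assumption.

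The stated 4.3% type I error and 80.1% power are correct and remain valid under the plan as written. They would fail only if unevaluable patients were replaced. The plan does not provide for replacement, but it does not rule it out either, so a sentence on this is worth adding.

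**What to change.** In the Group 2 ORR row of 13.2.1:

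- Define the primary population as every patient who received at least one dose of either agent.
- Count any such patient with no post-baseline assessment as a non-responder, whatever the reason.
- State that the 12 and 16 of the Simon rule are counted on this same set, and that treated patients who prove unevaluable are not replaced.
- Delete the compartment clause.
- Report the evaluable-only ORR as a sensitivity analysis.

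The design statements in 1.1.2, 5.2.2, 13.2.1, 13.2.2 and 13.2.4 refer to enrolled patients and should be aligned. Registrations cancelled before any treatment (section 4.4) would stay outside the set. The cost is one table row and short wording changes, with no new data or visits. The reported ORR may be slightly lower, and the stated error rates then apply to the population analysed.
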